Latinos currently represent 17% of the total U.S. population and the figure is expected to almost double by the year 2060²⁴ (NB: we use the term Latino to refer to individuals of Mexican, Puerto Rican, Cuban, Dominican, Central and South American, and Spanish descent). Although recognized as the country's largest ethnic minority group, there is ample evidence that Latinos experience circumstances that limit their access to culturally and linguistically appropriate evidence-based behavioral health treatments, compromising treatment outcomes^{2, 3, 25-27}. This is highly evident in our limited ability to adequately recognize and treat substance use among Spanish-speaking Latinos and alcohol use disorders in particular^{3, 28-30}. Latinos are more likely to engage in heavier drinking and binge drinking than non-Latino Whites, and when they enter treatment, they represent the ethnic minority group at highest risk for dropout³¹⁻³³. Acculturative stressors and socioeconomic disadvantage, particularly unstable housing and limited financial resources, have been associated with poor engagement and low treatment completion rates^{25, 31, 34-37}.

Despite some attention to patterns of substance use among Latinos, most available data focus on prevalence and treatment outcome among Latinos as one group, with very little information on the differences in rates of disorders and treatment outcomes across subgroups³⁸⁻⁴¹. Limited data about a growing, diverse and understudied population underscores the need for research that will shed light on the factors associated with alcohol treatment outcomes among Latinos^{42, 43}. The presence and severity of risk factors such as racism, discrimination, unemployment, and migration-related stress will vary among Latino subgroups; therefore, patterns of use, vulnerability to develop an alcohol use disorder, and treatment responses can also be expected to differ⁴⁴⁻⁴⁷. Understanding the influence of national origin, acculturation, patterns of

consumption and alcohol-related consequences among Latino subgroups is critical to advancing the field of health disparities research and improving treatment outcomes^{28, 37, 48-51}.

B. Why CBT?

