In years 3-5 of the proposed project, we will conduct a Stage 1 randomized clinical trial evaluating the program in which 90 Spanish-speaking individuals with alcohol use disorder will be randomized to (1) standard outpatient counseling at the Hispanic Clinic (ST; typically consisting of weekly individual and group supportive counseling) or (2) CBT4CBT-Spanish as an adjunct to ST. Other aspects of the trial will parallel those in our completed trial of the English version of CBT4CBT-Alcohol¹⁶ to facilitate comparability across studies. Treatments will be delivered over an 8-week period with a 6-month follow-up to assess durability and/or delayed emergence of treatment effects. The primary outcome measure will be percent days of

abstinence (PDA) by week. Secondary outcomes include percent heavy drinking days and number of individuals with no heavy drinking days in the last 4 weeks of treatment¹⁹.

2. Participants

Participants will be 90 individuals seeking treatment for alcohol use at the Hispanic Clinic of CMHC. The clinic treats a heterogeneous population, where 42% of those in the co-occurring treatment program report alcohol as their principal substance related issue and 43% are women. As reported above, we have demonstrated our ability to recruit, randomize, retain, and follow-up high numbers of closely related samples in this setting^{191, 192}.

a. Inclusion and exclusion criteria

Participants will be included who are (1) 18 years of age or older, (2) applying/referred for outpatient alcohol treatment, (3) meet current DSM-IV/DSM-5 criteria for alcohol use disorder with use in the past 30 days, (4) speak Spanish as their preferred or principal (most commonly spoken) language, (5) sufficiently stable for 8 weeks of outpatient treatment, and (6) willing to provide locator information and be contacted for follow-up for 6 months. Individuals will be excluded who (1) have an untreated/unstable bipolar or schizophrenic disorder, or (2) have a current legal case pending such that incarceration during the 8-week protocol is likely. Those physically dependent on alcohol can be rescreened following detoxification/stabilization (see Human Subjects).

b. Rationale for sample choice (also see Human Subjects section).

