c. Treatment phase

Treatment conditions are described below. Study treatments will last 8 weeks. During the treatment phase, all participants will complete weekly assessments, usually at the time they come in for treatment. Weekly breath and urine sample collection will be supervised by the research assistant. The research assistant conducting weekly and follow-up assessments will be blind to the participants' treatment assignment, using procedures we have worked out in previous trials¹¹².

- *Clinical deterioration.* We will closely monitor participant treatment response and safety in all conditions through weekly assessment sessions. These will include breath and urine screens with assessment of psychiatric status. Although in our experience this is a very rare event in behavioral trials¹¹⁹, including those of computer-assisted therapy^{14, 100}, participants who show significant deterioration (e.g., increased substance use or psychiatric symptoms that cannot be managed within the protocol) will be regarded as symptomatic failures, withdrawn from the treatment arm of the study, and referred appropriately, but will still be followed and included in the intent to treat analysis.
- *Strategies to minimize attrition.* In order to hold participant dropout to a minimum, we use multiple procedures recommended in our manual on enhancing compliance with substance abuse treatment^{205, 206}. These include rapid assignment to study treatments, thorough explanation of study treatments and requirements and a fully bilingual staff, close monitoring of participants' clinical status, integration of the research with the clinical program, accessibility of study staff for questions and problems, and adequate compensation to participants for the time spent on completing assessment instruments.

d. Termination and posttreatment assessment

At the end of the 8-week treatment period, all participants will be re-interviewed by the 'blind' research assistant, who will complete posttreatment ratings (see Assessments, below). Access to the CBT4CBT-Spanish-Alcohol program will be terminated for participants assigned to that condition. Participants in all conditions will be strongly encouraged to continue in treatment at their primary site (Hispanic Clinic, SATU, MAAS).

e. Follow-up

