Follow-up interviews will be conducted 1, 3, and 6 months after termination of treatment. Follow-up interviews will include the full posttreatment battery (see Assessments, below), including assessment of utilization of other treatments and services received. We will attempt to follow all participants in the intent to treat sample, regardless of their retention in treatment, using strategies that have been successful in multiple previous studies. These include: (a) thorough explanation at the initial consent interview to participants of the importance of follow-ups, (b) requiring that each participant provide at least 3 *verified* locators who are likely to have knowledge of their whereabouts throughout follow-up, (c) use of multiple sources and locators to track participants²⁰⁷, and (d) payment to participants of \$50 for each completed follow-up interview, with additional monetary incentives for completing consecutive interviews on time. Using these procedures, our current rate of follow-up approaches 90-98% across studies^{16, 126}. Thus, we have been successful in conducting true intent-to-treat analyses^{208, 209} in that the samples include post-treatment and follow-up data from all participants randomized, including those who have dropped out of treatment.

4. Treatments

a. Standard treatment as usual (ST)

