c. *Evaluation of treatment effects at posttreatment and follow-up*: The principal strategy for assessing the efficacy of the study treatments on outcome over time will be random effects regression models for continuously measured primary (e.g. percent days of abstinence by week) and secondary (e.g., acquisition of coping skills) outcome variables. The focus of the repeated measures analyses will be the 'contrast by time effects', which essentially evaluates whether the slopes, or rates of change, of one group differ from the slopes of another group. We have used these methods to evaluate main and interaction effects, with appropriate covariates (e.g., retention, compliance with treatment, time spent working with the CBT4CBT program) in multiple previous trials^{14, 151, 160, 200, 201, 254}. Follow-up data will be analyzed using random-effects regression modeling²⁵⁵ for our primary outcome measures across time, using the contrasts described above, with appropriate covariates (e.g., length of time in treatment, exposure to other treatment during follow-up). Random effects regression models have several advantages in follow-up data from clinical trials of substance users where participants are unlikely to attend follow-up evaluations precisely at the desired fixed points, and are less vulnerable than traditional MANOVA approaches to missing data^{208, 209, 251, 252}. As in our previous trials^{16, 126}, we estimate that our extensive efforts to track participants will yield a 90% follow-up rate.

d. *Adequacy of sample size*: This Stage 1 trial is intended to provide initial pilot testing and feasibility testing of the web-based CBT4CBT program in a Spanish-speaking sample of individuals with alcohol use disorder. Based on SSize software, the proposed sample sizes will enable us to detect effect sizes of .35 or higher for either hypothesis, which will be the criterion for determining whether CBT4CBT-Spanish-Alcohol has adequate promise to justify a fully powered randomized trial²⁵⁶. This sample size was sufficient for the English-language trials of the drug and alcohol versions of CBT4CBT, which yielded effect sizes of .46-.59^{13, 15, 16}.

Power calculations for random effects regression	Power	Estimated effect size	Estimated ICC	# of datapoints	Sample size per cell
H1: (CBt4CBT-S + ST) v ST, main effect for active treatment phase (assessed weekly, baseline-8weeks)	.80	.35	.40	9	45

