H2: (CBT4CBT-S + ST) vs ST, main effect for follow-up (assessed monthly, end of treatment-6 months)	.80	.50	.80	7	40

2. Treatment specificity and mediators

We will explore the extent to which participants improve coping skills over time using the ARRT as described above and the extent to which acquisition of coping skills may mediate outcome for CBT4CBT-Spanish-Alcohol in this sample. We have described our use of these models and strategies to evaluate treatment mediators in Preliminary Studies, above, and in several papers^{13, 105, 108, 151}. Following the general analytic framework outlined by Kraemer²⁵⁷, we will use the product of the coefficients method to evaluate the relationship between the mediator (e.g., acquisition of CBT-specific coping skills as measured by the ARRT), or indirect effect, and outcome^{155, 156, 258}. After running a regression equation to determine (1) the effect of treatment on the mediator (provides beta weight for a), we will evaluate (2) the strength of the relationship between the mediator, treatment, and outcome (provides beta b). Using MacKinnon's software PRODCLIN²⁵⁹, we will evaluate the asymmetric confidence intervals for the product of the regression estimates (a^*b).

SECTION VI: RESEARCH INVOLVING DRUGS, BIOLOGICS, PLACEBOS AND DEVICES

If this section (or one of its parts, A or B) is not applicable, state N/A and delete the rest of the section.

N/A

SECTION VII: HUMAN SUBJECTS

1. Subject Population:

Provide a detailed description of the types of human subjects who will be recruited into this study.

Participants will be individuals seeking outpatient treatment for alcohol use at the Connecticut Mental Health Center (CMHC), where the majority of clients are male (73%), middle aged (62%), unemployed (71%), unmarried (56%), and have not completed high school (64%). Spanish-speaking participants will be recruited from two CMHC outpatient programs (The Hispanic Clinic at [name] and the Substance Abuse Treatment Unit at [name]) or Connecticut Mental Health Center clinicians. Additionally, MAAS (The Multi- Cultural Ambulatory Addiction Service at [name]) has been appointed a recruitment site

2. Subject classification:

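### The H1 power of .80 at effect size .35 is approximated only by an undeclared one-sided .05 test; at two-sided .05 the row's own inputs give .68 before any data are missing.

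*Protocol*

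**What the plan says.** Protocol Section V.3.B.1 says that "90 Spanish-speaking individuals with alcohol use disorder will be randomized to" one of two arms. The allocation ratio is not stated, but 45 per cell implies 1:1.

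The power table in Section V.5.1.d has two rows:

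| Row | Label | Power | Effect | ICC | Datapoints | n per cell |
|---|---|---|---|---|---|---|
| H1 | "main effect for active treatment phase (assessed weekly, baseline-8weeks" | .80 | .35 | .40 | 9 | 45 |
| H2 | "main effect for follow-up (assessed monthly, end of treatment-6 months" | .80 | .50 | .80 | 7 | 40 |

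The text above the table claims that "the proposed sample sizes will enable us to detect effect sizes of .35 or higher for either hypothesis". It makes that effect size the criterion for whether the program merits a fully powered trial.

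On retention, Section V.5.1.c and the matching SAP section 1.c say "we estimate that our extensive efforts to track participants will yield a 90% follow-up rate". Section V.3.B.3.e reports that "our current rate of follow-up approaches 90-98% across studies". Section V.5.1.b and SAP section 1.b expect few missing participants and little missing data. They plan an intent-to-treat analysis by random effects regression. No rate is given for completing the weekly assessments, and I found no alpha or sidedness in either document.

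**The concern.** H1 tests the primary outcome, weekly percent days abstinent, and .35 is both the stated detectable effect and the threshold for going forward. A power figure cannot be interpreted without its alpha and sidedness. Here the missing convention decides whether .80 is roughly right or about 12 points too high.

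The row also has no margin. It counts every randomised participant at all nine points, although the plan expects some missing data. Weekly assessments take place "usually at the time they come in for treatment", so missed treatment visits could cost weekly data.

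What is at stake is how an H1 result is read. If the test is two-sided at .05, a true effect of .35 would be missed about one time in three, against the one in five that the table implies. A non-significant result would then be taken as stronger evidence against the program than it is.

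**Working it through.** **Inputs.** From the H1 row: effect d = .35 (in units of the total SD), ICC = .40, m = 9 points, n = 45 per cell. Assumed, because the documents do not say: alpha .05, compound symmetry (only an ICC is given) and a normal approximation. The quantity tested is the one the row names, a main effect averaged over the nine points.

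**Formulas.**
- Variance of a participant's mean over m points: V = ICC + (1 − ICC)/m
- SE of the arm difference: sqrt(2V/n)
- Power: Φ(d/SE − z), with z = 1.960 two-sided or 1.645 one-sided
- Detectable effect at .80 power: SE × (z + .8416)

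**1. The printed figure, complete data.** V = .40 + .60/9 = .4667. SE = sqrt(2 × .4667/45) = .1440. d/SE = 2.431.
- One-sided: Φ(2.431 − 1.645) = .78; detectable effect .1440 × 2.4865 = .36
- Two-sided: Φ(2.431 − 1.960) = .68; detectable effect .1440 × 2.8016 = .40

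Using the t distribution instead gives .78 and .67. The n needed for .80 at .35 is 2 × (z + .8416)² × .4667/.35², which is 47.1 per cell one-sided (48) or 59.8 two-sided (60).

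**2. Does H2 point to the same convention?** V = .80 + .20/7 = .8286. At n = 40, SE = .2035 and .50/SE = 2.457. Power is .79 one-sided or .69 two-sided. One-sided .05 with compound symmetry therefore comes near .80 in both rows. An AR(1) structure with two-sided .05 reproduces H2 (.80) but gives .93 for H1, so it does not fit both rows. No other convention tried does.

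**3. Adding missing data to H1.** Under compound symmetry a participant with m observed points contributes information 1/(.40 + .60/m): 2.143 at m = 9 and 1.000 at m = 1.
- 10% drop out, with the last observed point spread evenly over points 1 to 8: their mean information is 1.750, or .817 of a full record. Effective n = 45 × (.90 + .10 × .817) = 44.2.
- 10% give one point only: effective n = 45 × (.90 + .10/2.143) = 42.6.
- 10% give nothing: 45 × .90 = 40.5, taken as 40, the n in the H2 row. SE = .1528.

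| Data pattern, H1 at .35 | Power two-sided | Power one-sided | Detectable effect two-sided / one-sided |
|---|---|---|---|
| 45 complete | .68 | .78 | .40 / .36 |
| 10% dropout, partial data kept | .67 | .78 | .41 / .36 |
| 10% give one point only | .66 | .76 | not computed |
| 10% give no data (40 per cell) | .63 | .74 | .43 / .38 |

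Sidedness is worth about 10 points. Missing data costs about 1 point under partial-data dropout, and 4 to 5 points in the extreme case.

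**The case against.** A reader might infer that attrition causes the shortfall: H2 is set at 90% of 45, H1 is not, and so H1 should be recalculated at 40 per cell. The documents do not support this, for three reasons.

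- The plan never derives 40. It is consistent with 45 × .90 = 40.5, but the 90% is a follow-up rate stated for the follow-up phase. Using a different n for an 8-week and a 6-month phase is not in itself a contradiction.
- The planned model keeps partial records. The nine points include baseline, and the Timeline Follow-Back is scheduled at screening. Few participants would therefore contribute nothing, and 40 complete cases is a worst case rather than what the analysis would produce.
- The Background remark that among Latinos entering treatment "they represent the ethnic minority group at highest risk for dropout" concerns leaving treatment, not missing outcomes. The protocol follows participants regardless of retention. It also repeats the Timeline Follow-Back after treatment, so a missed weekly visit is not shown to be a lost weekly value.

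It can also be said that .78 is close enough to .80, and that other models do better. With AR(1) correlation, two-sided power is .93 at 45 per cell. With eight post-baseline means adjusted for baseline it is .84. The first point stands if the test is one-sided, but then the plan has to say so. The second shows that the result depends on the model. However, neither document describes those models, and the table gives an ICC and counts baseline among its nine points.

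Finally, this is a Stage 1 trial. Its go-forward criterion is stated as an effect size without reference to significance, and the earlier trials cited had effects of .46 to .59. That limits the consequence. It does not make the printed power right.

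**Conclusion.** The point holds in this form: H1's .80 at .35 rests on complete data from all 90 participants and on an undeclared test convention. It is approximated one-sided (.78) and not delivered two-sided (.68). The gap exists before any loss. Allowing for 10% dropout under the planned model moves the figures only to about .67 and .78, and even the extreme case gives .63 and .74.

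This rests on alpha .05, compound symmetry and the main effect that the table names. The analysis text puts its focus on differences in slope, which the table does not power. That is a separate matter and is not assessed here. The direction of the two-sided conclusion would change under AR(1) correlation or baseline adjustment, which is a further reason to state the basis of the calculation.

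**What to change.** In Protocol V.5.1.d, state for H1 the alpha, the sidedness, the correlation structure and the missing-data assumption. Keep 45 per cell, with partial data retained under the random effects model. Then do one of two things:

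- print the power that results at .35, about .67 two-sided or .78 one-sided; or
- keep .80 and print the detectable effect, about .41 two-sided or .36 one-sided.

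Change the H1 part of the sentence claiming .35 or higher to match. If the sponsor intends a different model, such as one adjusted for baseline, describe it and recompute on that basis. H1 should not be reset to 40 per cell, since that would describe an analysis the trial does not plan.

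The change affects two or three table cells and one sentence. Enrolment stays at 90 and no visits are added. The only downside is a less favourable stated figure.

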5. Rates of recruitment of women, minorities, and children with respect to targets.

These reports are generated by the Data Manager each quarter and signed by each study PI prior to their submission to the DSMB. DSMB comments are documented and forwarded to the Yale IRB at the time of the annual review and re-approval.

Because the projected effect sizes may not be large enough for detection during interim analyses, we are not proposing a preliminary analysis of accumulating efficacy and safety data by treatment assignment. Instead, we propose to submit a quarterly report of aggregate data to the DSMB members that contains screening data, baseline demographics, retention data, serious adverse events data, as well as accrual status including projections, times to milestones, and any other data that will help in the assessment of the clinical trial. Based on this report, each DSMB member will complete a form making one of two recommendations: 1) continue recruitment as planned; or 2) schedule formal DSMB meeting immediately. If any DSMB member recommends a meeting, this will be scheduled within one week, minutes will be kept, the report will be reviewed with the PI, and the committee will vote on whether the study should: 1) continue recruitment unchanged; 2) continue with a protocol amendment; 3) stop recruiting pending further investigation. If, after this meeting, any DSMB member votes to stop recruitment or requests a protocol modification, the Yale IRB will be informed.

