Participants who experience a significant psychiatric or medical problem requiring an overnight hospitalization at an acute care facility will be considered to have experienced an SAE. In general, most SAEs will result in inpatient care and thus in transfer to the inpatient division of CMHC. All SAEs will result in the completion of an SAE Form and a verbal report within one hour to the Principal Investigator ([name]) and the clinic directors (Drs. [name], [name]). Within 24 hours, the following additional individuals will be informed: 1) all co-investigators; and 2) the DSMB. Adverse events that are serious and unanticipated and probably, possibly, or definitely related or adverse events occurring with greater frequency than anticipated will be reported to the Yale Human Investigation Committee within 48 hours of discovery. The procedures for SAE reporting include written documentation using the clinical notes related to the adverse event and specific forms detailing the event with a sign-off by all appropriate supervisory personnel. Communication of recommendations and decisions from all parties (DSMB, Yale Human Investigations Committee, and CMHC Administration) are made back to the investigator in a timely manner. We will report all protocol amendments or changes in the informed consent form to NIDA as well as any temporary or permanent suspension of patient accrual.

4. Confidentiality & Security of Data:

- a. What protected health information (medical information along with the HIPAA identifiers) about subjects will be collected and used for the research?

In Phase 1, no PHI will be collected. In Phase 2, PHI that will be collected includes names, addresses, phone numbers, and email addresses for locator purposes.

Our study assessments/forms have been designed to avoid collecting identifiable information (e.g., no PHI identifiers are collected on CRFs). The only dates collected are

protocol session dates. These are changed to 'number of sessions completed' when data sets are anonymized and released to other investigators.

b. How will the research data be collected, recorded and stored?

Research data are collected on CRFs, and sent to data managers in our research offices on a closed secure network. All computers used by research staff are password protected. No identifying information is on CRFs. Only authorized individuals will have access to CRFs.

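### The plan rules out by-arm review of safety data for a reason that fits only the efficacy tests, so the routine DSMB report is pooled

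*Protocol*

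**What the plan says.** Protocol Section IX.3 (Data and Safety Monitoring Plan) gives a reason, "Because the projected effect sizes may not be large enough for detection during interim analyses", and then the decision: "we are not proposing a preliminary analysis of accumulating efficacy and safety data by treatment assignment". In place of such an analysis, "we propose to submit a quarterly report of aggregate data to the DSMB members". The listed contents include retention and SAE data, and the standard form covers AEs and SAEs. Neither list mentions arm. Each member uses the report to recommend continuing or meeting. Every study PI signs it before it goes to the DSMB, and at a meeting it is gone through with the PI.

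The same section has other safety routes:

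- After an SAE: "Within 24 hours, the following additional individuals will be informed: 1) all co-investigators; and 2) the DSMB". Whether the notice gives the arm is not stated.
- "If any DSMB member recommends a meeting, this will be scheduled within one week".
- Serious, unanticipated events judged at least possibly related go to the Human Investigation Committee (HIC), and "adverse events occurring with greater frequency than anticipated will be reported to the Yale Human Investigation Committee within 48 hours of discovery". No anticipated frequency is given.

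The SAE definition is narrow: a participant with a "significant psychiatric or medical problem requiring an overnight hospitalization at an acute care facility will be considered to have experienced an SAE". Section V.3.B.3.c separately provides for withdrawing participants from study treatment for clinical deterioration, which it calls very rare.

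On effect sizes, Section V.5, 1.d says "the proposed sample sizes will enable us to detect effect sizes of .35 or higher for either hypothesis". Its table uses .35 for H1 (treatment phase) and .50 for H2 (follow-up).

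**The concern.** One sentence treats two different activities alike. An interim efficacy comparison is a test: it needs power and, if acted on, error control. A safety count by arm is a description and needs neither. The stated reason concerns detecting projected effects, and the plan projects none for safety.

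If events rise during the trial, the DSMB's first question will be whether the program is responsible or whether the sample in both arms is sicker than expected. The two call for different action. Randomisation provides that comparison from data already collected, and the routine report as described leaves it out. The gap is widest for a participant withdrawn for deterioration without an overnight stay. That is not an SAE, so no individual notice to the DSMB is described, and the case would appear only in pooled AE or retention figures. The conflict-of-interest statement also names quarterly DSMB review as one safeguard for a product whose copyright holder has an ownership interest in its distributor.

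**Working it through.** **1. Is the stated reason sound for efficacy?** Inputs from the H1 row in Section V.5: effect size .35, ICC .40, 9 datapoints, 45 per cell, power .80. Alpha and sidedness are not given, so 0.05 is assumed, both one- and two-sided.

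- Variance factor for the mean of 9 measures: (1 + 8 × .40)/9 = .467.
- Standardised difference at 45 per arm: .35/√(2 × .467/45) = 2.43. Power is Φ(2.43 − 1.645) = .78 one-sided and Φ(2.43 − 1.96) = .68 two-sided. The stated .80 is approximately reproduced one-sided.
- At 22 per arm: .35/√(2 × .467/22) = 1.70. Power is .52 one-sided and .40 two-sided.

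An interim efficacy test would be weak, so the reason holds there.

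**2. Does it carry over to safety?** Both projected effect sizes are drinking-outcome contrasts, and no event rate or safety effect is projected. A formal safety test would be weak too: at assumed rates of 2% v 15% with 45 per arm, Fisher's exact test has power .45. A count by arm is not a test, so low power is no ground for omitting it.

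**3. What does a pooled count hide, and how often would it matter?** The documents give no event rates, so all rates here are assumptions, written ST v CBT4CBT. Totals are the sum of two independent binomials, computed exactly.

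| Per arm | Rates | Expected events | P(3 or more) | P(4 or more) | P(6 or more) |
|---|---|---|---|---|---|
| 22 | 1% v 9% | 2.2 | .38 | .17 | .02 |
| 22 | 5% v 5% | 2.2 | .38 | .18 | .02 |
| 22 | 2% v 2% | 0.9 | .06 | .01 | <.001 |
| 45 | 1% v 9% | 4.5 | .84 | .67 | .29 |
| 45 | 5% v 5% | 4.5 | .83 | .66 | .29 |
| 45 | 2% v 2% | 1.8 | .27 | .11 | .01 |

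Harm confined to one arm (1% v 9%) and a sicker sample in both (5% v 5%) give almost the same pooled distribution, because the expected totals are equal: 22 × (.01 + .09) = 22 × (.05 + .05) = 2.2.

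The split does separate them. Take four events at 22 per arm:

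- Equal rates: P(all four in CBT4CBT) = C(22,4)/C(44,4) = 7,315/135,751 = .05.
- 1% v 9%: P(none in ST) = .99^22 = .802. P(four in CBT4CBT) = 7,315 × .09^4 × .91^18 = .088. P(total of four) = .110. The conditional probability is .802 × .088/.110 = .64.

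But a total of exactly four has probability only .11 in either case at that stage.

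**The case against.** The case on the other side is substantial.

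- **Rare events, large assumed harm.** The protocol rates overall risk as minimal and deterioration as very rare. The 1% v 9% scenario is a nine-fold increase for a web program added to usual care, and nothing in the documents suggests it. At rates near 2% the table would usually be almost empty. This stands, and it limits the weight of the point.
- **Other routes exist.** SAE notices reach the DSMB individually, any member can force a meeting, relatedness is judged for HIC reporting, and the quarterly report includes baseline demographics, which bear partly on sample mix. This stands as mitigation. None of these routes is stated to give counts by arm, and the clause allowing other helpful data follows a sentence that excludes by-arm analysis.
- **Small counts mislead.** An excess of three or more events in CBT4CBT at full accrual arises by chance with probability .03 at 2% per arm and .11 at 5%. This stands, and argues for a descriptive table without a trigger.

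A reader might infer two stronger claims. One is that the DSMB is barred from learning the arm. The text declines to propose a by-arm analysis; it does not forbid the DSMB from asking for assignments, and it leaves open whether the SAE notice shows the arm. The other is that safety will never be compared by arm, even at the end. The statistical sections seen here name no such table, but part of the SAP was removed before review, so its absence cannot be established.

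**Conclusion.** The point holds in a limited form. The protocol makes a stated choice to exclude by-arm safety review, and its reason covers only efficacy. The routine quarterly report is therefore pooled and does not by itself show the source of SAEs or deterioration withdrawals. That rests on reading aggregate as pooled across arms, the natural sense after a sentence excluding analysis by assignment.

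The importance is at the low end of minor. At half accrual, totals large enough for the split to inform are uncommon even under the large assumed harm, and rare at 2% per arm. The case for change is that the information is nearly free, not that harm is likely. Nothing here affects the validity of the primary analysis.

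**What to change.** 1. In Section IX.3, limit the exclusion to efficacy: no efficacy outcome will be reviewed by treatment assignment during the trial.
2. Add a closed section to each quarterly report, by coded arm (A/B): number randomised, participants with at least one SAE, and participants withdrawn from study treatment for clinical deterioration. Keep it descriptive, with no test and no numeric trigger; the existing rule that any member may call a meeting is enough.
3. Amend two rules in the same section. The PI signature before submission, and the review of the report with the PI at a meeting, should cover only the open, pooled section. The Data Manager sends the closed section directly to the DSMB. Without this amendment, item 2 contradicts the protocol.
4. Put the coded arm on the DSMB's copy of the 24-hour SAE notice, but not on the co-investigators' copy.

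The cost is protocol wording and one short table per quarter from data already collected. Sample size, alpha, power and the primary analysis stay as they are. There are three downsides. The closed section must be kept from the PIs. Withdrawal for deterioration is a staff judgement in an open-label trial, so its counts can differ by arm without real harm. Small splits can also be over-read, so the table should carry a note to that effect.
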